### **Methodology**

### **Study Setting:**

This study will be conducted in International Youth Centre, Cheras. It has been the main focal point of where most of the courses have been conducted. It is within easy reach and centrally located near Hospital UKM. Many participants will come from all around Malaysia to attend. The centre is equipped with a lecture hall and boarding for the participants.

## **Study Design:**

This is a pre-post quasi-experimental study that will be conducted over 12 months duration. Participants in this study will undergo a House Officer (HO) preparatory course. The level of confidence, readiness and psychological wellbeing will be evaluated. There will be three assessment time points: at baseline (before the course), immediately after the course (only for level of confidence and readiness) and 1 month after working as HO. This study is unable to have a control because of constraints in resources.

### **Study Duration:**

This study will start from April 2018 - March 2019

#### **Sampling of participants:** Recruitment

Participants who attend the Medicorp HO Preparatory Course from April 2018 –March 2019 will be recruited into this study as the sampling frame. The eligibility criteria are based on the following:

Inclusion Criteria

1. Participants that have registered to attend the Medicorp HO Preparatory Course

**Exclusion** Criteria

- 1. Participants declared to have psychiatric illness
- 2. Participants who have not completed a medical degree (medical students)
- 3. Participants already working as a HO

The sampling methods employed in this study will be taking all participants who fulfil the eligibility criteria and agree to participate in this study.

### Intervention:

The intervention in this study will be the Medicorp HO preparatory course which comprises of a 3 day training touching on aspects of HO training that is needed practically for a HO to function. The training will touch on the nature of the HO job, explaining about technical details such as the shift and on call system. The tagging period, and assessments that HOs need to undergo during their training. They will be guided on how to clerk, review and present common as well as emergency cases. Other aspects involved in clerking such as common forms used in the wards and also how to refer cases is also discussed. Apart from that, soft skills such as communication among staff, financed, balancing social life and future career planning is incorporated in the training. There are hands on training for participants for common procedures such as continuous bladder drainage insertion and venepuncture. The trainers are specialists, specialists in training, medical officers, and also house officers who come to share their experience. Medicorp encourages their alumni to be part of their training program. This module will be held on a 1-2 monthly basis. The Module Content is moderated by Medicorp based on discussions with board of directors, advisors and feedback from participants. The training program are done as lecture, tutorial and hands on session. Before commencing the course, participants will be included in a whatsapp group, for easier content sharing and updates of the course. They will continue this networking even after completion of this course. They will be also be guided in the online applications of their job through this application and also through Facebook. During the commencement of their job, Medicorp will use their database to guide them into different whatsapp groups according to their place of work for additional support.

### Study outcome measures:

### 1. Primary outcome

a. Level of confidence:

This will be adapted from the IMU Student Competency Survey (Appendix 2) as there are no published studies on the confidence level of medical graduates before beginning HO-ship. The questionnaire comprises of 5 sections. The first 4 sections asses on generic skills, practical tasks, soft skills and their confidence as a whole, using a Likert scale assessment. Scoring is a mean score of 1-5 and the higher the score, the higher the confidence. The last section asks on the one daunting aspect of being a HO out of a list of 7 things, this section is descriptive.

#### 2. Secondary outcome

a. Readiness

This is also adapted from the IMU competency survey and is asked on a likert scale of 1 to 5 for their level of readiness. It is assessed after the confidence section. The higher the score, the higher the level of readiness.

b. Psychological wellbeing

This is using the Depression Anxiety Stress Scale (DASS): This questionnaire is used to asses Depression, Anxiety and Stress. It uses a likert scale. The scores indicate normal, mild, moderate, severe and extremely severe for each of the domains. The higher the scores, indicates the more severe the conditions.

Each of the three DASS-21 scales contains 7 items, divided into subscales with similar content. The depression scale assesses dysphoria, hopelessness, devaluation of life, self-deprecation, lack of interest / involvement, anhedonia and inertia. The anxiety scale assesses autonomic arousal, skeletal muscle effects, situational anxiety, and subjective experience of anxious affect. The stress scale is sensitive to levels of chronic non-specific arousal. It assesses difficulty relaxing, nervous arousal, and being easily upset / agitated, irritable / over-reactive and impatient. Scores for depression, anxiety and stress are calculated by summing the scores for the relevant items.

The DASS-21 is based on a dimensional rather than a categorical conception of psychological disorder. The assumption on which the DASS-21 development was based (and which was confirmed by the research data) is that the differences between the depression, anxiety and the stress experienced by normal subjects and clinical populations are essentially differences of degree. The DASS-21 therefore has no direct implications for the allocation of patients to discrete diagnostic categories postulated in classificatory systems such as the DSM and ICD. (Lovibond & Lovibond, 1995)

### Sample size

Sample size was calculated using G\*Power 3.1 sample size calculator software. Based on reports by confidence score from a study analysing pre and post emergency department posting in junior doctors was used. The mean overall confidence score was 56.475(24.67) at the end of month 1 and 62.775(28.69) at the end of month 4(Williams et al., 1997). The estimated sample size was 208 participants after accounting for power of 80%, significance level of 0.05% and 30% attrition.

### **Instruments & Data Collection**

### Intervention: The Medicorp HO Preparatory Module

### Tools for assessment:

### 1. Baseline questionnaire

The study instrument will be a set of questionnaire that will be divided into sections A-E.

The English versions will be used.

a) Socio-demographic data :

This will include certain details of participants such as:

- Age
- Sex
- Religion
- Ethnicity
- Year of graduation
- University of Graduation
- Marital status
- Place of work (evaluation during 1 month post HO-ship)

### a) Clinical Experience:

This will be adapted from the IMU Student Competency Survey. This will show participants past clinical experience on common procedures during their undergraduate years.

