### b) *Confidence level:*

Adapted from the IMU student competency questionnaire as explained in study outcome measures

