## 2. Post course questionnaire (immediate)

- a) Level of confidence
- b) Readiness

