#### 3. Case report form

Conducted via telephone call at 1 month after starting work as HO Content will include:

- a) Level of confidence
- b) Readiness
- c) DASS
- d) Work place information: which hospital and posting
- e) Any suggestions to improve the course based on your current working experience?

All the questionnaires will be pilot tested by testing this on 30 medical graduates before using the questionnaire.

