#### **Data collection**

A pre-tested self-administered questionnaire which includes baseline socio-demography, adaptation of the IMU Student Competency Survey, and the Depression Anxiety Stress Scale will be used. 1 month follow-up will be done by telephone. After the participants have completed the course, their level of readiness and confidence will again be assessed via a self-administered questionnaire. This will be done on the last day of the course.

The participants will later be followed up 1 month after they have been working as a HO in their respective hospitals. The organisers will keep track of placements of all participants via social media applications as part of the course is still maintaining connections and informal training after the course has ended and as participants start the process of job application and working.

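### As listed, clinical experience is asked just before confidence at baseline but on neither later form, so an order effect could not be separated from a course effect

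*Combined protocol and SAP*

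**What the plan says.** Under Instruments & Data Collection, the entry for the baseline questionnaire reads "The study instrument will be a set of questionnaire that will be divided into sections A-E". Five components follow: socio-demographic data, clinical experience, confidence, readiness and DASS. The clinical-experience section is taken from the same student survey as the confidence scale, and its stated purpose is "This will show participants past clinical experience on common procedures during their undergraduate years". Confidence is the next entry. On readiness, the secondary-outcome section says "It is assessed after the confidence section".

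The immediate post-course questionnaire lists two components, confidence and then readiness. The 1-month case report form lists confidence, readiness, DASS, workplace and suggestions, and is "Conducted via telephone call at 1 month after starting work as HO". Neither later form lists a clinical-experience section.

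On mode, the Data collection section says that after the course "their level of readiness and confidence will again be assessed via a self-administered questionnaire", as at baseline. Confidence is the primary outcome: "Scoring is a mean score of 1-5 and the higher the score, the higher the confidence". Study Design states that there is no control group, and Data Analysis judges effectiveness by within-group change across the three time points.

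**The concern.** Answers to a rating can depend on what was asked just before it. Here the preceding section is close in content to the outcome: it asks about experience of common procedures, and the confidence scale has its own section on practical tasks. The protocol's literature review itself links perceived lack of skills to lack of confidence, so a prompt about experience could plausibly move the rating.

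In a controlled trial such a shift would affect both arms and largely cancel. In this design it does not. Every effectiveness statement is a later score minus the baseline score, so a shift in the baseline alone passes in full into the change in confidence, and possibly into readiness, which is asked next. Controlling for baseline, as Data Analysis plans, cannot correct this, because the baseline is the measurement affected. A larger sample does not help either, since this is bias and not noise. The pilot in 30 graduates is not described as examining item order.

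**Working it through.** **1. Order of components, as listed.**

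| Time | Listed before confidence | Listed after confidence | Mode |
|---|---|---|---|
| Baseline | Socio-demographics, clinical experience | Readiness, DASS | Self-administered |
| End of course | Nothing | Readiness | Self-administered |
| 1 month in post | Nothing | Readiness, DASS, workplace, suggestions | Telephone |

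Five listed components match the five sections A to E, and the remark that readiness follows confidence agrees with the list. That makes the list the natural reading of the order of administration, but it does not prove it. Between baseline and end of course the mode is the same and the preceding items differ. Between baseline and 1 month the preceding items, the mode and the respondent's work experience all differ.

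**2. The plan's own sample size, to fix the inputs.** The Sample size section gives 56.475 (SD 24.67) and 62.775 (SD 28.69), a difference of 6.30. The pre-post correlation r is not stated. With r = 0.5 assumed:

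- SD of the difference = √(24.67² + 28.69² − 2 × 0.5 × 24.67 × 28.69) = √(608.61 + 823.12 − 707.78) = 26.91
- standardised difference = 6.30 / 26.91 = 0.234
- a paired t-test at two-sided 5% and 80% power needs 146 completers
- 146 / 0.70 = 208.6, which agrees with the plan's 208 apart from rounding

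This takes the significance level as 5%, as in Data Analysis; the Sample size section prints 0.05%, which at r = 0.5 would need 496. Some other combinations of assumptions also land near 208, so r = 0.5 is not established, and r = 0.8 is carried as a second case (SD of the difference 17.30).

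**3. What an assumed shift would do if the course were inert.** The documents give no size for a context effect. Let s be the baseline shift in units of the baseline SD.

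- shift in points = s × 24.67
- share of the planned change = s × 24.67 / 6.30
- noncentrality = (s × 24.67 / SD of the difference) × √n
- rejection rate from the noncentral t distribution with n − 1 degrees of freedom, two-sided 5%

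For s = 0.10, r = 0.5, n = 208: 2.467 / 26.91 = 0.0917; 0.0917 × √208 = 1.32; rejection rate 26%.

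| s | Points | Share of 6.30 | n=208, r=0.5 | n=208, r=0.8 | n=146, r=0.5 | n=146, r=0.8 |
|---|---|---|---|---|---|---|
| 0.05 | 1.23 | 20% | 10% | 18% | 9% | 14% |
| 0.10 | 2.47 | 39% | 26% | 53% | 20% | 40% |
| 0.20 | 4.93 | 78% | 75% | 98% | 60% | 93% |

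The nominal rate is 5%. The n=208 columns suit the immediate contrast, measured on the last day of a 3-day course, if almost nobody is lost. The n=146 columns apply after the planned 30% attrition. The rates hold for a shift in either direction. A lowered baseline produces a spurious gain; a raised baseline produces a spurious loss, or hides the same number of points of a real gain.

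**The case against.** **The order is inferred.** The list describes content, and nothing in it assigns the components to sections A to E. The remark on readiness fixes only readiness relative to confidence and says nothing about where clinical experience sits. The questionnaire itself is not in the text available for review. This stands, and the point is therefore conditional on the printed form.

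**The direction is open.** A reader might infer that participants list procedures they have never done, that this lowers their baseline confidence, and that the bias favours the course. The documents do not support that. The section is said to show past experience; no item format is given and undone procedures are not mentioned. Participants already hold a medical degree, and recalling procedures they have performed could raise baseline confidence and work against the course.

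**The extra effect may be small.** Respondents rate practical tasks within the confidence scale at all three times, and the score also averages generic and soft skills, which a section on procedures touches less directly. Only the additional effect of that section differs at baseline. This stands, and it argues against assuming a large shift.

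**The figures are hypothetical.** The shift sizes are assumptions. The 6.30-point benchmark comes from another study's score, not from this trial's 1 to 5 mean. The calculation uses a paired t-test, whereas the plan uses a three-time repeated measures ANOVA. All of this stands; the table shows sensitivity and is not evidence that a shift exists.

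**Re-ordering does not clean up the 1-month contrast.** That is correct. The change to telephone and the month of work remain.

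**The section has a purpose.** It serves the first specific objective. It still does so at the end of the form.

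**Conclusion.** The point holds in conditional form. As listed, clinical experience precedes the confidence rating at baseline and at neither later assessment. If the printed form follows that order, any resulting shift, of unknown size and in either direction, cannot be separated from a course effect, because there is no control group and the analysis is within-group. The immediate contrast is where this can be isolated and where re-ordering removes it.

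The 26% to 53% at n=208, and 20% to 40% with 146 completers, rest on an assumed shift of 0.10 baseline SD, assumed correlations of 0.5 and 0.8, planning SDs from another study, and a paired t-test. They show that a modest shift could matter, not that one is present. It would go too far to conclude that the result will be biased in the course's favour, or that re-ordering would make the 1-month score comparable with baseline. Next to the absent control group and the change of mode, this is a minor to moderate matter, worth acting on because the remedy is nearly free.

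**What to change.** Check the printed baseline form. In the baseline questionnaire section of the protocol, state the order of administration: confidence, readiness and DASS first, in the same order as on the two later forms, with clinical experience and socio-demographic data moved to the end. No item is added or dropped, and the first specific objective is still met. If the printed form already runs this way, one sentence saying so settles the point.

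The cost is re-ordering the form before the pilot; no additional data, staff or participants are needed. If data have already been collected in the listed order, report the difference in preceding items between baseline and the later assessments as a limitation, with direction and size unknown. For the 1-month comparison, the change to telephone and the intervening month of work need to be acknowledged in either case.

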### b) *Confidence level:*

Adapted from the IMU student competency questionnaire as explained in study outcome measures

## c) Readiness :

Adapted from the IMU student competency questionnaire as explained in study outcome measures

## d) Psychological well – being :

DASS as explained in study outcome measures

## 2. Post course questionnaire (immediate)

- a) Level of confidence
- b) Readiness

#### 3. Case report form

Conducted via telephone call at 1 month after starting work as HO Content will include:

- a) Level of confidence
- b) Readiness
- c) DASS
- d) Work place information: which hospital and posting
- e) Any suggestions to improve the course based on your current working experience?

All the questionnaires will be pilot tested by testing this on 30 medical graduates before using the questionnaire.

#### **Data collection**

A pre-tested self-administered questionnaire which includes baseline socio-demography, adaptation of the IMU Student Competency Survey, and the Depression Anxiety Stress Scale will be used. 1 month follow-up will be done by telephone. After the participants have completed the course, their level of readiness and confidence will again be assessed via a self-administered questionnaire. This will be done on the last day of the course.

The participants will later be followed up 1 month after they have been working as a HO in their respective hospitals. The organisers will keep track of placements of all participants via social media applications as part of the course is still maintaining connections and informal training after the course has ended and as participants start the process of job application and working.

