## Specific

- To determine the socio-demographic and past clinical experience of participants attending Medicorp's HO Preparatory Course
- 2. To determine the level of confidence, readiness, and psychological well-being of participants to work as a HO before attending the Medicorp HO Preparatory course
- 3. To determine the level of confidence and readiness of participants to work as a HO after immediately attending the Medicorp HO Preparatory course
- 4. To determine the level of confidence, readiness and psychological well-being of participants to work after 1 month working as a HO
- To determine the effectiveness of the Medicorp HO Preparatory course on the level of confidence, readiness and psychological well-being before attending the course and after 1 month working as a HO
- 6. To determine the determine the effectiveness of the Medicorp HO Preparatory course on the level of confidence and readiness immediately after attending the course

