## **Study Hypothesis**

- The HO Preparatory Course is an effective module in improving the confidence level, readiness and psychological well-being of participants in preparing them for HO-ship in Malaysia
- 2. The level of confidence, readiness, and psychological well-being of participants to work as a HO before attending the Medicorp HO Preparatory course is low
- 3. There is a high level of confidence and readiness of participants to work as a HO after attending the Medicorp HO Preparatory
- 4. There is a high level of confidence, readiness and psychological well-being of participants to work after 1 month working as a HO

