#### **Data Analysis**

The data will be analysed using IBM Social Package for Social Science (SPSS) version 24. A descriptive analysis of the demographic characteristics of the participants, clinical experience and baseline level of confidence, readiness and psychological wellbeing will be reported using means and standard deviations (SD) or median and inter-quartile range (IQR) for continuous variables (depending on the data distribution) and as frequencies and percentages for categorical data. An analysis to compare between participants who completed and withdrew from the study will be made using Chi-square or Exact test (for unbalanced data) for categorical variables and independent t-test for continuous data.

A repeated measures ANOVA will be conducted to determine the effectiveness of the intervention within the groups across the study periods (baseline, immediately after intervention and at 1 month after working). Controlling for baseline measures will be done to determine the change over time on the measured outcomes (level of confidence, readiness and psychological wellbeing). All analyses conducted are two-tailed with significant level set at p value <0.05.

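### Outcomes are self-completed at baseline but taken by telephone at 1 month, so with one group any mode effect cannot be separated from the change to 1 month

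*Combined protocol and SAP*

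**What the plan says.** The Data collection section describes the baseline instrument as self-administered. It holds the sociodemographic items, the adapted competency survey (the source of confidence and readiness) and DASS. On the last course day, "their level of readiness and confidence will again be assessed via a self-administered questionnaire". For the final assessment the same section says "1 month follow-up will be done by telephone". The Case report form item agrees: "Conducted via telephone call at 1 month after starting work as HO", with confidence, readiness and DASS among its contents.

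Study Design gives the later two time points as "immediately after the course (only for level of confidence and readiness) and 1 month after working as HO", so DASS is measured only at baseline and 1 month. It adds: "This study is unable to have a control because of constraints in resources".

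Under Data Analysis, "A repeated measures ANOVA will be conducted to determine the effectiveness of the intervention within the groups across the study periods". No term for mode and no comparison of modes is planned. The questionnaires are piloted on 30 graduates, but the pilot is not described as comparing written with telephone answers.

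**The concern.** Every participant changes mode at the same visit. A difference between that visit and an earlier one contains whatever happened to the participant plus whatever comes from answering aloud to a caller instead of on a form. The outcomes are self-ratings of confidence, readiness, depression, anxiety and stress.

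The results at stake are:

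- the fifth specific objective, which compares the outcomes "before attending the course and after 1 month working as a HO";
- the step from course end to 1 month within the repeated measures ANOVA;
- every DASS change, since no DASS change is measured in a single mode;
- the fourth hypothesis, "There is a high level of confidence, readiness and psychological well-being of participants to work after 1 month working as a HO", which concerns a level known only by telephone.

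The sixth objective, baseline to immediately after the course, uses one mode and is not affected.

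**Working it through.** **Mode by visit**

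| Visit | Confidence, readiness | DASS |
|---|---|---|
| Baseline | self-completed | self-completed |
| Last course day | self-completed | not measured |
| 1 month in post | telephone | telephone |

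A telephone indicator equals 1 at 1 month and 0 otherwise, for everyone. It is identical to the indicator for the 1-month visit, so the two coefficients cannot be estimated separately at any sample size. Controlling for baseline measures, as Data Analysis proposes, does not help, because baseline has one mode only. This conclusion needs no assumed number.

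**The plan's own figure**

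Inputs from Sample size: means (SD) 56.475 (24.67) and 62.775 (28.69), 80% power, 30% attrition, total 208. Alpha is printed as 0.05% and read here as 0.05 two-sided, as in Data Analysis. The within-person correlation r is not stated.

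- Difference: 62.775 − 56.475 = 6.3.
- Planned effect in SD units: 6.3 / √((24.67² + 28.69²)/2) = 6.3 / 26.756 = 0.235.
- SD of the difference: √(24.67² + 28.69² − 2r × 24.67 × 28.69).
- At r = 0.5: SD 26.91, dz = 6.3/26.91 = 0.234, n = 146 by paired t-test, and 146/0.70 = 208.6, close to the stated 208.
- At r = 0.3: n = 202 and 202/0.70 = 289 after rounding up. At r = 0.7: n = 90 and 90/0.70 = 129 after rounding up.
- The match at 0.5 is not unique. At r = 0.45, n = 160 and 160 × 1.3 = 208. A range of r is therefore shown below.

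**Illustration: mode shift with no true change**

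Completers: 208 × 0.70 = 145.6, taken as 146. The calculation is a paired t-test on the two-point contrast, two-sided 0.05, with equal SDs and dz = shift/√(2(1 − r)). It is not the three-point ANOVA. The shift sizes and r are assumptions.

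| Assumed mode shift | r = 0.3 | r = 0.5 | r = 0.7 |
|---|---|---|---|
| 0.1 SD: dz | 0.085 | 0.100 | 0.129 |
| 0.1 SD: share with p<0.05 | 17% | 22% | 34% |
| 0.2 SD: dz | 0.169 | 0.200 | 0.258 |
| 0.2 SD: share with p<0.05 | 53% | 67% | 87% |

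With no shift the share is 5%. A shift could also work against a real gain. If 0.1 SD opposes a true 0.235 SD, then dz = 0.135/√(2(1 − r)). Power falls from about 67%, 81% and 95% to about 28%, 37% and 56% at r = 0.3, 0.5 and 0.7.

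**The case against.** The strongest reply is that nothing in the documents shows that a mode effect exists. A reader might infer that telephone answers will flatter the course, or that the 1-month results are known to be biased. Neither is supported, because no size or direction is given and every shift above is assumed. What stands is narrower: this design could never show whether such an effect is present.

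A second reply is that the 1-month contrast is already confounded by starting work and by repeat testing, and that the protocol admits it has no control. That is correct and limits the gain. But starting work is inherent in the follow-up and the control group is ruled out by resources, whereas the mode is a choice that can be changed. Matching the mode also helps the 1-month levels, which are descriptive and need no control.

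A third reply points to the Budget, which pays an enumerator for three questionnaires per participant. A reader might take this to mean interviews throughout. The line does not say so, and Data collection says the first two forms are self-administered.

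Finally, self-completion with a telephone fallback replaces one 1-month mode by two, depending on who responds, among newly employed doctors in different hospitals. This is a real drawback. An analysis of self-completers alone would mix mode with response selection and would not isolate mode.

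**Conclusion.** The point holds as a structural one. Mode is completely confounded with the 1-month visit for all three outcomes. This reaches the fifth objective, the step from course end to 1 month, every DASS change and the level asserted in the fourth hypothesis. The sixth objective is clear of it, so it would be wrong to infer that all the study's comparisons are affected.

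The true size cannot be computed from the documents. The illustration shows only that a shift smaller than the planned 0.235 SD would matter. That planned effect itself comes from another population and another scale than the 1 to 5 mean score used here.

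A reader might also infer that matching the mode would let the 1-month change be credited to the course, or would hold false claims of effectiveness to 5%. It would do neither, since starting work and repeat testing remain in the contrast. The change is worth making as a cheap reduction of one avoidable bias.

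**What to change.** In the Case report form item and in Data collection:

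1. Make the self-administered form used at baseline the first route for confidence, readiness and DASS at 1 month, sent through the existing participant contact channels and returned to the research team.
2. Keep the planned call as the reminder, and as the fallback for those who do not return the form.
3. Record the mode of each 1-month form.
4. Report the 1-month contrast overall and in self-completers, stating that the latter are a selected subset and that the comparison does not isolate mode.
5. State that the research team reviews returned DASS forms, so that the referral commitment under Ethical considerations still operates.

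If the telephone is kept for everyone, name mode as a limitation of every 1-month contrast and of the fourth hypothesis. That costs a sentence but leaves the bias in place.

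The cost is low but not nil: reminders, review of returned forms, possibly slower return, and two modes at 1 month. If the 1-month form is online, a paper/online difference remains. The form already exists. The Budget already holds RM150 for calls (150/260 = RM0.58 per participant) and an enumerator line for three questionnaires (260 × 3 × RM10 = RM7,800), which includes the 1-month one. A participant reached only by the fallback call is measured as under the present plan.
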